**Table 3 Dose Modification Guidance for Grade 3 Non-hematologic Toxicities, Except Liver Dysfunction**

| Occurrence | Acalabrutinib Action   |
|------------|--|
| First      | Withhold acalabrutinib until recovery to Grade $\leq 2$ or baseline. Then, restart acalabrutinib at the same dose (Table 1).                           |
| Second     | Withhold acalabrutinib until recovery to Grade $\leq 2$ or baseline. Then, restart acalabrutinib with 1 level dose reduction or discontinue (Table 1). |
| Third      | Withhold acalabrutinib until recovery to Grade $\leq 2$ or baseline. Then, restart acalabrutinib with 1 level dose reduction or discontinue (Table 1). |

### **8.4 Management of Acalabrutinib-Related Adverse Events**

Management for acalabrutinib-related AEs are located in Appendix H.

## **9. RESPONSE EVALUATIONS AND MEASUREMENTS**

### **9.1 Progression-free Survival**

Progression-free survival is defined as the time from Day 0 of BMT until the date of objective radiological PD according to RECIL or death (by any cause in the absence of PD). Patients who are alive and free from PD will be censored at the date of last tumor assessment. Patients who begin subsequent therapy prior to PD or death will be censored at the date of last tumor assessment prior to the start of subsequent therapy.

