## **2. STUDY OBJECTIVES**

### **2.1 Primary Objective**

The primary objective of this study is to:

- Determine the PFS rate of subjects who received at least one dose of acalabrutinib and are alive and free of PD or relapse 2 years post-BMT.

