### **6.5.9 Fresh Lymphoma Biopsy Sample**

When feasible, collection of a lymphoma biopsy at relapse is encouraged, but will not be considered a protocol deviation if the patient withdraws consent. This sample will be used to investigate changes in pathway signaling and potential mechanisms of resistance (i.e., genetic alterations or evidence of alternative pathway activation). For this reason, a relapse lymphoma biopsy is encouraged in patients who achieve an objective response to the study drug, but later relapse.

All fresh lymphoma biopsies will be formalin-fixed and paraffin-embedded slides. Failure to obtain a sufficient lymphoma sample after making best efforts to biopsy the lymphoma will not be considered a protocol deviation.

If additional lymphoma molecular profiling is required to further understand any response to the study drug, the Sponsor may request a sample of the most recent lymphoma biopsy for additional research.

The results of this exploratory research will be reported separately and will not form part of the clinical study report (CSR).

Details of sample collection, processing, shipping, and storage will be described in the laboratory manual.

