### **10.2 Sample Size Considerations**

The primary endpoint is the percentage of patients who are alive and free of PD or relapse at 2 years post-BMT. A sample size of 45 patients produces a two-sided 95% CI of 65%-90% when the observed percentage is 80%. To account for a 10% non-evaluable rate, the total sample size will be 50 patients.

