#### **10.4.2 Efficacy Analysis**

All efficacy analyses will be performed using the Efficacy Analysis Set.

- PFS is defined as the time from Day 0 of BMT to objective radiological PD or death on study. PFS will be evaluated as Kaplan-Meier estimates of the percentage of subjects who receive at least one dose of study drug and who are alive and free of PD or relapse at 2 years post-BMT according to RECIL (Younes et al 2017). Data for subjects who are still alive and free from progression at the time of data cut-off date, are lost to follow-up, have discontinued the study, or have initiated a subsequent protocol therapy will be censored on last assessment (or, if no post-baseline tumor assessment, at the time of first dose plus 1 day). Approximate 95% CI for median duration of PFS will be computed using the formula proposed by Brookmeyer and Crowley.
- Minimal residual disease status will be examined by NGS on all bone marrow aspirate and blood samples collected up to 2 years post-BMT to determine the conversion rate from MRD+ to MRD while taking acalabrutinib, correlate MRD status with PFS, and identify mutations that correlate with disease relapse. An MRD status will be defined as all results from whole blood and BM that are negative for the presence of residual clonal cells (with assay sensitivity of 10^-6). An MRD+ status will be defined as all results from whole blood or BM that are positive for residual clonal cells per Adaptive Biotechnologies' reporting methods.

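### The primary endpoint is freedom from PD or relapse, but only radiological PD or death counts as an event, so a pathology-proven relapse without imaging change can go uncounted and raise the 2-year rate

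*Combined protocol and SAP*

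**What the plan says.** **Objective and endpoint.** Section 2.1 asks for the rate of treated subjects who "are alive and free of PD or relapse 2 years post-BMT". Section 10.1 repeats this, and Section 10.2 sizes the trial on it: "The primary endpoint is the percentage of patients who are alive and free of PD or relapse at 2 years post-BMT". Relapse is named beside PD each time but is not defined anywhere.

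**Operative event.** Section 9.1 measures PFS from Day 0 of transplant "until the date of objective radiological PD according to RECIL or death (by any cause in the absence of PD"). Section 10.4.2 gives the same event: "PFS is defined as the time from Day 0 of BMT to objective radiological PD or death on study". Its next sentence describes the Kaplan-Meier percentage of subjects "alive and free of PD or relapse at 2 years post-BMT according to RECIL", which attaches relapse to RECIL.

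**RECIL as reproduced.** In Appendix E, PD needs growth of target lesions, regrowth of a small node past a size limit, or a new lesion. The bone marrow row sets no condition for PD. Appendix F adds progression of nontarget lesions.

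**Censoring.** Section 9.1: "Patients who begin subsequent therapy prior to PD or death will be censored at the date of last tumor assessment" before that therapy began. Section 10.4.2 has a similar rule. Appendix D schedules scans at Day 80-100 and at 6, 12, 18 and 24 months.

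**Other evidence.** Section 6.5.9: "When feasible, collection of a lymphoma biopsy at relapse is encouraged". Section 6.5.13 schedules marrow at Day +100 and at 1 year, for MRD.

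**The concern.** The objective names two kinds of failure besides death, and the event definition recognises one, by imaging only. The excluded kind is a lymphoma relapse shown by pathology while the scans do not change.

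Elsewhere the protocol does not confine progression to imaging. Exclusion 3 in Section 3.3 refers to confirmed clinical PD. Section 8.1 lets clinical, laboratory and/or radiologic assessments settle whether PD has truly occurred after a dose interruption. Section 11.3.1 accepts any appropriate method of documenting progression, with RECIL as an example. Section 9.2 requires a clean marrow to confirm CR. The same patient could therefore have progressed under Section 8.1 or 11.3.1 and have no event under Section 9.1.

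The censoring rule makes this matter. A patient treated because the lymphoma came back is censored for a reason tied directly to the outcome, and Kaplan-Meier handles that patient as if the future risk were the same as for those still in remission. The trial has one arm, so no control group shares the distortion.

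**Working it through.** **1. The plan's own figure.** Section 10.2 has 45 evaluable patients, an observed 80% and a two-sided 95% interval of 65%-90%. Since 0.80 × 45 = 36, the exact (Clopper-Pearson) interval for 36/45 is 65.4%-90.4%, which agrees. The total also agrees: 45/0.90 = 50. The synopsis prints 95% as the upper limit; that does not reproduce and is a separate matter.

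**2. What the rules do to one patient.** Take a patient with a clean 12-month scan and a relapse at month 14 shown by marrow morphology, with no imaging change.

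- *New therapy starts before RECIL PD or death:* censored at the 12-month scan, before the relapse. With scans 6 months apart, the gap can reach about 6 months.
- *No new therapy, alive, no RECIL PD through month 24:* event-free at 2 years.
- *RECIL PD or death by month 24, before any new therapy:* counted, but later than the relapse. With follow-up otherwise complete, the 24-month rate is unchanged.

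The first two routes raise the estimate and the third leaves it alone.

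**3. Size.** Use 45 patients, 9 true failures by 24 months, 36 event-free and no other censoring. Let *k* of the 9 be relapses that the rule does not count.

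- If every failure counts: 36/45 = 80.0%.
- Lowest biased value, with all *k* censored before any counted event. The 9 − *k* events then fall in a risk set that starts at 45 − *k*, and the Kaplan-Meier product collapses to 36/(45 − *k*).
- Highest biased value, with all *k* censored after the counted events or left event-free: (36 + *k*)/45.

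| *k* (share of the 9) | Lowest | Highest |
|---|---|---|
| 0 | 36/45 = 80.0% | 36/45 = 80.0% |
| 1 (11%) | 36/44 = 81.8% | 37/45 = 82.2% |
| 2 (22%) | 36/43 = 83.7% | 38/45 = 84.4% |
| 3 (33%) | 36/42 = 85.7% | 39/45 = 86.7% |

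Every ordering of events and censorings was enumerated, and all results fall within these limits. The shift is about 2 percentage points per uncounted relapse.

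**4. The reverse view.** If a reported 36/45 included two such relapses among the patients counted as event-free, the rate in the sense of the objective would be 34/45 = 75.6%. Section 1.3 cites 76% (95% CI 64%-85%) as the 2-year PFS in a transplant study with rituximab maintenance. This gives scale only; the plan specifies no comparison with that figure.

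**The case against.** **The wording can be reconciled.** Section 10.4.2 ties PD or relapse to RECIL. For a patient in remission, a new lesion under Appendices E and F can serve as the relapse criterion, and objective and definition then agree. This stands, so a reader who inferred an irreconcilable contradiction would go too far. It does not close the gap: on this reading too, a pathologically proven relapse without imaging change is uncounted, and the plan does not say that this is intended.

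**The size is assumed.** This also stands. The documents give no frequency for such relapses, and a patient with RECIL PD or death by 24 months and no prior new therapy is still counted. A shift of about 2 points per patient is modest beside a planned interval of 65%-90%, and there is no null rate or efficacy threshold for it to cross.

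**Appendix E does not say that marrow disease can never be PD.** Correct. The marrow row sets no condition once PD is met, and the table does not address marrow disease as a new or nontarget lesion. The narrower point holds: neither appendix gives an explicit route to PD from marrow, blood or biopsy alone, and the word radiological in Sections 9.1 and 10.4.2 works against inferring one.

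**The trial does not already collect all the evidence.** Also correct. The only scheduled on-treatment marrow is the 1-year MRD sample. A CBC with differential is not a lymphoma work-up. Biopsy at relapse is encouraged rather than required, and its exploratory results stay out of the clinical study report.

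**A wider event could overlap with MRD.** Section 1.2 lists flow cytometry among the techniques that reveal MRD. Counting any flow positivity would build MRD into PFS and make the secondary MRD-PFS correlation partly circular. The fix has to exclude this.

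**Conclusion.** The concern holds as a gap between the endpoint named and the event counted. Under Sections 9.1 and 10.4.2, a relapse proven by pathology without imaging change is either censored at an earlier scan, left event-free, or counted only if RECIL PD or death follows before new therapy. With otherwise complete follow-up, the 2-year rate can be unchanged or too high, but not too low.

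On the plan's own 45 patients and 80%, one to three such relapses give about 82%, 84% or 86-87%. This rests on an assumed number of relapses, on their never being counted by 24 months, and on no other censoring. If none occur, the effect is zero.

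A reader might infer that the reported rate will be inflated. The documents do not support that; they show only that the rule permits it and in which direction. The documents as supplied contain no sensitivity analysis that would reveal it. Section 10.4 leaves fuller detail to the analysis plan, but the event itself is already fixed in the two sections cited. This should be fixed before results are known; it does not undermine the design.

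**What to change.** In Sections 9.1 and 10.4.2:

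1. Define the event as the first of: PD by RECIL; relapse confirmed by histology, cytology, or marrow or blood morphology with immunohistochemistry, dated at the sample; or death from any cause.
2. State that MRD positivity alone, or low-level flow cytometry positivity alone, is not an event.
3. Apply the subsequent-therapy censoring rule only after this event rule, so that a confirmed relapse before new therapy counts as a failure.
4. Record the basis of relapse (imaging, pathology or both) in the eCRF.
5. Report the radiological-only definition as a sensitivity analysis.

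If the sponsor prefers the radiological event as primary, the objective and endpoint should say so, and the wider definition should become the sensitivity analysis.

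**Cost.** Wording in two sections and an eCRF item; the eCRF is not among the documents, so that effort cannot be checked. No new scheduled procedure is needed. The rate may be slightly less favourable. Pathology outside the schedule is triggered by the investigator, so ascertainment may differ across the roughly 10 sites; the radiological-only analysis shows how much depends on it.

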### **3.4 Discontinuation from Study Drug**

Patients will be discontinued from the study drug for any of the following reasons:

- PD
- Completed treatment
- Start of alternative anticancer therapy
- Irreversible or intolerable toxicity or abnormal laboratory values thought to be related to drug toxicity
- Conditions requiring therapeutic intervention not permitted by the protocol
- Intercurrent illness (this will be at the Investigator's discretion)
- Inability of the patient to comply with study requirements
- Patient requests to discontinue treatment
- Patient withdraws consent from the study or study participation altogether
- Patient lost to follow-up
- Pregnancy
- Study termination

After discontinuation from protocol treatment, patients must be followed for AEs for 30 days after their last dose of study drug. All new AEs occurring during this period must be reported and followed until resolution, unless, in the opinion of the Investigator, these values are not likely to improve because of the underlying disease. In this case, the Investigator must record his or her reasoning for this decision in the patient's medical records.

All patients who have Grade 3 or 4 laboratory abnormalities (per National Cancer Institute Common Terminology Criteria for Adverse Events [NCI CTCAE] Version 5.0) at the time of discontinuation must be followed until the laboratory values have returned to Grade 1 or 2, unless it is, in the opinion of the Investigator, not likely that these values are to improve. In this case, the Investigator must record his or her reasoning for making this decision in the patient's medical records.

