## 5.1 Treatment Plan

In this clinical trial, the study drug only refers to acalabrutinib. The BMT is a non-investigational medicinal product and is not the study drug.

Acalabrutinib 129 mg will be self-administered orally BID on a 28-day schedule, with or without food, until the patient has reached approximately 2 years post-BMT.

Acalabrutinib will be administered until PD, unacceptable toxicity, or the subject discontinues treatment for any other reason.

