### **11.3.4      Deaths**

Deaths that occur during the protocol-specified AE reporting period that are attributed by the Investigator solely to PD will be recorded on the “End of Study” eCRF screen. All other on-study deaths, regardless of attribution, will be recorded on an SAE Report Form and expeditiously reported to the Innovations Safety Department.

When recording an SAE with an outcome of death, the event or condition that caused or contributed to the fatal outcome should be recorded as the single medical concept on the SAE Report Form and AE eCRF screen. If the cause of death is unknown and cannot be ascertained at the time of reporting, record “Death NOS” (“death cause unknown”) on the AE eCRF screen. During post-study survival follow-up, deaths attributed to PD will be recorded on the “Follow-up Summary” and “Death Page” eCRF screens.

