### **13.3.1 Confidentiality**

#### **13.3.1.1 Patient Confidentiality**

Confidentiality of patients' personal data will be protected in accordance with the Health Insurance Portability and Accountability Act of 1996 (HIPAA). HIPAA regulations require that, in order to participate in the study, a patient must sign an authorization form for the study that he or she has been informed of the following:

- What PHI will be collected from patients in this study
- Who will have access to that information and why
- Who will use or disclose that information
- That health information may be further disclosed by the recipients of the information, and that if the information is disclosed the information may no longer be protected by federal or state privacy laws
- That the information collected about the research study will be kept separate from the patient's medical records, but the patient will be able to obtain the research records after the conclusion of the study
- Whether the authorization contains an expiration date

- The rights of a research patient to revoke his or her authorization.

In the event that a patient revokes authorization to collect or use his or her PHI, the Investigator, by regulation, retains the ability to use all information collected prior to the revocation of patient authorization. For patients that have revoked authorization to collect or use PHI, attempts should be made to obtain permission to collect at least vital status (e.g., that the patient is alive) at the end of their scheduled study period.

In compliance with ICH GCP guidelines and applicable parts of 21 CFR it is a requirement that the Investigator and institution permit authorized representatives of Innovations, the regulatory authorities, and the IRB direct access to review the patient's original medical records at the site for verification of study-related procedures and data.

One measure to protect confidentiality is that only a unique study number will identify patients in the eCRF or other documents submitted to Innovations. This information, together with the patient's year of birth, will be used in the database for patient identification. Patient names or addresses will not be entered in the eCRF. No material bearing a patient's name will be kept on file by Innovations. Patients will be informed of their rights within the ICF.

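### Sections 9.1 and 10.4.2 define the primary PFS endpoint differently: a known death after a patient leaves the study is an event under 9.1 and censored under 10.4.2

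*Combined protocol and SAP*

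**What the plan says.** Section 9.1 measures PFS from Day 0 of BMT to the "date of objective radiological PD according to RECIL or death (by any cause in the absence of PD"). It censors only two groups: patients alive and progression-free, at their last tumor assessment, and patients who start subsequent therapy before an event, who are "censored at the date of last tumor assessment prior to the start of subsequent therapy".

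Section 10.4.2 specifies the Kaplan-Meier analysis of the 2-year percentage, which is the primary endpoint. It restates the end of PFS as "objective radiological PD or death on study". Besides patients event-free at data cut-off, it says that patients who "are lost to follow-up, have discontinued the study, or have initiated a subsequent protocol therapy will be censored on last assessment". A parenthesis then sends patients without a post-baseline tumor assessment to the day after first dose. Section 9.1 has no such rule.

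Section 10.4 leaves the full analysis description to the SAP and does not rank the two sections.

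**The concern.** A primary endpoint needs one event definition. Here a programmer working from 9.1 and another working from 10.4.2 could code the same patient differently, each correctly.

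The firm conflict is over death. Section 9.1 places no limit on where or when the death occurs. Section 10.4.2 limits it to deaths on study, a term it does not define, and separately lists leaving the study as a reason to censor. Counting such deaths as censored can only raise the 2-year estimate relative to 9.1. Those deaths may also be related to the disease, so the censoring may be informative.

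The documents allow for vital status to be learned after a patient leaves. Section 11.3.4 says: "During post-study survival follow-up, deaths attributed to PD will be recorded on the" dedicated eCRF screens. Section 13.3.1.1 says that after authorization is revoked "attempts should be made to obtain permission to collect at least vital status". In an open-label, single-arm trial, the choice between the two rules is best fixed before outcomes are reviewed.

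**Working it through.** **Step 1. The two rule sets applied to the same hypothetical patients.**

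| Patient | Section 9.1 | Section 10.4.2 |
|---|---|---|
| A. Leaves the study progression-free at month 10, no new therapy, known to have died at month 20 | Event at month 20 | Censored at last assessment |
| B. Starts other anticancer therapy progression-free at month 10, progresses or dies at month 16 | Censored at last tumor assessment before month 10 | If 'protocol' is a slip: censored, but the date is not limited to before the therapy. Read literally: event at month 16 |
| C. Alive, progression-free, lost to follow-up | Censored at last tumor assessment | Same |
| D. No event, no post-baseline tumor assessment | No specific rule; the last scan is the Day 80-100 scan | Censored at first dose plus 1 day |

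A is a plain contradiction. B depends on how 10.4.2 is read. C agrees. D differs only slightly in date, since dosing starts around Day 100. It should also be rare, because the Efficacy Analysis Set in Section 10.3 requires an adequate post-baseline assessment unless the patient discontinued for death or PD.

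**Step 2. The plan's own figure.** Section 10.2 gives n = 45, 80% observed and a two-sided 95% CI of 65%-90%. With 36/45 = 80.0%, the exact (Clopper-Pearson) interval is 65.4%-90.4%, which reproduces it. The conflict does not affect this figure.

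**Step 3. Size of the death conflict.** Take 45 patients, of whom 9 fail before 2 years under 9.1 and 36 are event-free at 2 years. Suppose k of the 9 are deaths after leaving the study, which 10.4.2 censors at an earlier scan.

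- If all k are censored before the first remaining event, 45 - k patients are at risk and 9 - k fail, so the estimate is 36/(45 - k).
- If all k are censored after the last remaining event, the estimate is 1 - (9 - k)/45 = (36 + k)/45.

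Other timings fall between these bounds.

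| k | 9.1 | 10.4.2, lower bound | 10.4.2, upper bound |
|---|---|---|---|
| 0 | 80.0% | 36/45 = 80.0% | 36/45 = 80.0% |
| 1 | 80.0% | 36/44 = 81.8% | 37/45 = 82.2% |
| 2 | 80.0% | 36/43 = 83.7% | 38/45 = 84.4% |
| 3 | 80.0% | 36/42 = 85.7% | 39/45 = 86.7% |

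A simulation with failures spread evenly over months 4-24, censoring the k deaths at the last scheduled scan before death, gives means of 82.0%, 84.0% and 86.0% for k = 1, 2 and 3. These lie inside the bounds. The values of k are assumed, because the documents give no frequency.

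**The case against.** **The evidence that such deaths will be known is thin.** The sentence in 11.3.4 concerns deaths attributed to PD, and many of those patients would already have had a PFS event. Section 13.3.1.1 covers only revoked authorization, needs fresh permission, and gives as its example that the patient is alive. Overall survival is not an objective. This stands, but it bears on how often patient A occurs, not on whether the sections agree.

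**On study could be read broadly,** to cover the whole follow-up of up to 5 years. That narrows the gap. It does not close it, because 10.4.2 still names leaving the study as a reason to censor.

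**Stronger readings that the documents do not support.**

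- *That 10.4.2 ignores new therapy and so keeps later events.* Read literally, its clause covers nobody: Section 5.1 says "In this clinical trial, the study drug only refers to acalabrutinib", while Section 3.4 lists "Start of alternative anticancer therapy" as a separate reason to stop study drug. A clause that covers nobody is more probably a slip for any subsequent therapy. Section 6.4.6 also ends the follow-up visits at new anticancer therapy, so later progression may not be captured. That section is written for visits from 2 years onward, and Section 5 promises PFS follow-up for all subjects, so this limit is not certain.
- *That the last assessment in 10.4.2 could be any assessment.* The parenthesis that follows speaks of tumor assessment, so that is the natural meaning. What remains is that 10.4.2 does not limit the date to before the new therapy.
- *That relapse in the objective is undefined.* Section 10.4.2 ties progression or relapse to RECIL.
- *That the rule will be chosen after the data are seen.* Section 10.4 defers detail to the SAP, which may settle it. No SAP text among the documents available for this review does so.

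**Conclusion.** The point holds for deaths after study discontinuation. The two definitions of the primary endpoint contradict each other there, and no available text says which applies. The subsequent-therapy wording, the missing limit on the censoring date and the rule found only in 10.4.2 are secondary mismatches, to be corrected in the same edit.

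The size is about 2 points of 2-year PFS per affected patient, assuming 45 evaluable patients and 9 failures. That is small beside a planned interval 25 points wide (65%-90%), and there is no success threshold for it to cross. It is not evidence that the reported result will be biased: with no such patient, the death conflict has no effect. It should be corrected because it concerns the primary endpoint and costs little, but it does not undermine the design.

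**What to change.** Before the primary analysis, put one definition in 9.1, 10.4.2 and the SAP.

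- **Event:** the first of RECIL progression or death from any cause, including known deaths after study discontinuation, unless subsequent anti-lymphoma therapy started first.
- **Censoring, no known progression or death** (including patients lost to follow-up or who left the study): last tumor assessment.
- **Censoring, any subsequent anti-lymphoma therapy before progression or death:** last tumor assessment before that therapy.
- **Censoring, no event and no post-baseline tumor assessment:** first dose plus 1 day.

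In 10.4.2, delete 'on study' and 'protocol', and adopt the 9.1 wording for the censoring date when new therapy starts. Restrict the loss-to-follow-up and study-discontinuation clauses to patients with no known progression or death. Without that restriction, deleting 'on study' leaves the contradiction in place. A sensitivity analysis that counts new anti-lymphoma therapy as an event is optional.

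The cost is wording. The start date of new therapy is already needed for the 9.1 rule, and no visit, scan or sample-size change follows. There are two downsides. Reported 2-year PFS may be slightly lower than under 10.4.2. Deaths after leaving the study may also be ascertained more readily than continued event-free status, which could pull the estimate down.
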